1.4.2. Nonclinical Pharmacokinetics

Repotrectinib was highly bound (> 95%) to human serum albumin. The primary route of elimination of repotrectinib was CYP (cytochrome P450) 3A4-mediated metabolism, followed by glucuronidation of the oxidative metabolites, which were subsequently excreted into bile and urine. Repotrectinib weakly inhibited CYP enzymes with insignificant time-dependent inhibition. The only UGT (uridine 5'-diphospho-glucuronosyltransferase) inhibited by repotrectinib was UGT1A1. Human hepatocyte culture studies suggested that repotrectinib may induce CYP2B6 and CYP3A4(5) enzymes. Repotrectinib was transported by P-glycoprotein (P-gp), and likely by breast cancer resistance protein (BCRP) and multidrug and toxin extrusion protein (MATE) 2-K. However, repotrectinib was not a substrate for any other human solute carrier (SLC) transporters evaluated. Repotrectinib inhibited P-gp, BCRP, organic anion-transporting polypeptide (OATP) 1B1, OAT3, MATE1 and MATE2-K.

1.4.3. Nonclinical Toxicology

In accordance with the ICH S9 Guideline “Nonclinical Evaluation for Anticancer Pharmaceuticals” (March 2010), the Sponsor has completed a comprehensive nonclinical safety program encompassing *in vitro* hERG assay, ECG assessment in monkeys, single- and repeat-dose exploratory toxicology studies, and definitive 28-day and 91-day toxicology studies with

28-day recovery periods conducted in rat and monkey, as well as genotoxicity and phototoxicity studies.

The nonclinical profile was well-characterized with adequate exposure margins to support the intended use of repotrectinib for patients with advanced solid tumors.

1.5. Clinical Experience

Repotrectinib is currently under evaluation in a Phase 1/2 clinical trial as a monotherapy in subjects with advanced or metastatic solid tumors harboring *ROS1*, *NTRK1-3*, or *ALK* rearrangements (TPX-0005-01 or TRIDENT-1). Repotrectinib is also being evaluated as a monotherapy in a clinical study of pediatric subjects and young adults with advanced or metastatic solid tumors harboring *ROS1*, *NTRK1-3*, or *ALK* alterations (TPX-0005-07).

Based on the safety, preliminary efficacy, and PK data obtained in Phase 1 of TRIDENT-1 (data cutoff of March 2019), the recommended Phase 2 dose (RP2D) was determined to be:

- 160 mg once daily (QD) for the first 14 days and may increase to 160 mg twice a day (BID) based on subject safety and tolerability. Subjects must meet the following criteria while on 160 mg QD prior to dose increase to 160 mg BID: no evidence of grade ≥ 3 treatment-related adverse event (TRAE), unmanageable grade ≥ 2 dizziness, ataxia or paresthesia; or grade ≥ 3 clinically significant lab abnormalities.

Repotrectinib absorption was relatively fast under fasting conditions, with a median time to reach maximum (peak) plasma drug concentration (T_{max}) of 2 hours. Mean C_{max} and AUC_{inf} increased after a single dose with increasing doses from 40 mg QD to 240 mg QD. Apparent volume of distribution (V_z/F) was medium with geometric mean values ranging from 229 to 506 L.

Geometric mean oral clearance (CL/F) was low compared to human liver blood flow, ranging from 8.9 to 16.1 L/h. Mean terminal half-life was long after a single dose, ranging from 14.6 to 25.9 hours. The accumulation ratio (R_{acc}) values of C_{max} and AUC were lower than expected based on the single-dose terminal half-lives. The CL/F at steady state was higher than observed after a single dose at the same administered dose, suggesting a possible auto-induction of metabolic enzyme(s).

Overall, at the time of the most recent safety data cutoff (30 October 2020), 185 subjects have received at least one dose of repotrectinib in doses ranging from 40 mg QD to 200 mg BID in the TRIDENT-1 study. In the Phase 1 portion, the MTD was not reached. There were 4 dose-limiting toxicities (DLTs): 1 DLT of dizziness at 240 mg QD and 3 DLTs at 160 mg BID (2 DLTs of dizziness; 1 DLT of dyspnea and hypoxia).

Of the 185 subjects enrolled in the TRIDENT-1 study as of the 30 October 2020 safety data cutoff date, 180 (97.3%) subjects experienced at least one treatment-emergent adverse event (TEAE), with approximately half of the TEAEs reported with a maximum severity of grade 1 and 2 and the majority managed without dose modifications.

The most common TEAEs occurring in $\geq 20\%$ of subjects regardless of relationship to study drug included dizziness (58.4%); dysgeusia (43.2%); constipation (32.4%); dyspnea (31.4%); fatigue (27.0%); paresthesia (25.4%); anemia (22.2%); and nausea (20.0%). TEAEs (grade ≥ 3) were experienced by 93 (50.3%) of 185 subjects. Dizziness (grade ≥ 3) occurred in 4 subjects (2.2%).

Dizziness (9 [5%] subjects) was the most common reason for dose interruption. The majority (80%) of dizziness events have been grade 1, and no subjects discontinued treatment due to dizziness.

In summary, safety data from the Phase 1 and Phase 2 patient populations of TRIDENT-1 demonstrate a favorable tolerability profile for repotrectinib.

1.5.1. Study TPX-0005-09: Mass Balance, Pharmacokinetics, and Metabolism of Repotrectinib in Healthy Male Subjects

TPX-0005-09 was conducted as a 2-part, 2-treatment, fixed-sequence study in 7 healthy male volunteers to investigate the mass balance, PK, and metabolism of a single oral dose and PK of an intravenous tracer of [¹⁴C]repotrectinib in healthy male subjects. The treatments were administered after an overnight fast of at least 10 hours. Below is a summary of key findings. Refer to the Investigator's Brochure for further details.

Following concomitant administration of a single oral dose of 160-mg repotrectinib capsule formulation and intravenous administration of tracer [¹⁴C]repotrectinib in study TPX-0005-09 (Period 1), the geometric mean absolute bioavailability of repotrectinib based on AUC_{0-∞} was approximately 45.7%. The geometric means t_{1/2} of the IV formulation and the oral capsule dose were 32.5 and 36.2 hours, respectively.

Following oral administration of a 160 mg of [¹⁴C]repotrectinib (100 μCi) dose (TPX-0005-09, Period 2), the mean total recovery of radioactivity in excreta was 93.7% with radioactivity recoveries in feces and urine of 88.8% and 4.84%, respectively. No metabolite exceeded 10% of total circulating drug-related radioactivity. All detected metabolites had been previously detected in rat and/or cynomolgus monkey following oral administration; therefore, there were no unique human metabolites.

1.6. Proposed Clinical Starting Dose

1.6.1. Repotrectinib in Combination with Trametinib

Repotrectinib is an oral, adenosine triphosphate (ATP)-competitive potent kinase inhibitor with activity against JAK2, SRC, and FAK. Among 185 subjects treated in the Phase 1 and Phase 2 portions of the TRIDENT-1 study, the most common toxicities observed were dizziness (58.4%), dysgeusia (43.2%), constipation (32.4%), dyspnea (31.4%), fatigue (27.0%), paresthesia (25.4%), anemia (22.2%), and nausea (20.0%). The majority of dizziness events were grade 1 or grade 2 and generally occurred within the first 14 days of treatment. A titration approach was implemented to minimize early onset of TEAEs, including dizziness, thus the RP2D of repotrectinib is 160 mg QD for the first 14 days, after which the dose may be increased to 160 mg BID based on subject safety and tolerability.

Trametinib is a MEK inhibitor indicated as monotherapy for the treatment of patients with metastatic melanoma with BRAF V600E or V600K mutations and in combination with dabrafenib for the treatment of patients with metastatic NSCLC harboring a BRAF V600E mutation. The most common adverse events (≥ 20%) seen with trametinib as a single agent include rash, diarrhea, and lymphedema ([Mekinist® \[trametinib\] USPI 2020](#)).

Based on the known toxicity profiles of both repotrectinib and trametinib described above, overlapping toxicities are not anticipated. However, in clinical trials, development of combination therapies of targeted agents can prove to be challenging because of toxicities observed with combined treatments, even if individual agents do not have overlapping toxicities. Therefore, the starting dose of repotrectinib in combination with trametinib for the Phase 1b dose escalation portion of the study will be 120 mg daily (QD), and the starting dose of trametinib will be 2 mg QD.

Further doses will be explored during the dose escalation, and the RP2D for repotrectinib given in combination with trametinib will be chosen based on the results from the Phase 1b portion of the study.

2. STUDY OBJECTIVES

2.1. Phase 1b Objectives

2.1.1. Primary Objectives

- Evaluate the safety and tolerability of repotrectinib at increasing dose levels in combination with trametinib for the treatment of subjects with locally advanced or metastatic *KRAS*-mutant solid tumors.
- Determine the maximum tolerated dose (MTD) and/or recommended Phase 2 dose (RP2D) of repotrectinib in combination with trametinib for the treatment of subjects with locally advanced or metastatic *KRAS*-mutant solid tumors.

2.1.2. Secondary Objectives

- Characterize the pharmacokinetic (PK) profile of repotrectinib in combination with trametinib.
- Describe the preliminary efficacy of repotrectinib in combination with trametinib.

2.2. Phase 2 Objectives

2.2.1. Primary Objective

- Evaluate the efficacy of repotrectinib in combination with trametinib for the treatment of subjects with locally advanced or metastatic *KRAS*-mutant solid tumors as measured by objective response rate (ORR).

2.2.2. Secondary Objective

- Evaluate the efficacy of repotrectinib in combination with trametinib for the treatment of subjects with locally advanced or metastatic *KRAS*-mutant solid tumors as measured by clinical benefit rate (CBR), progression-free survival (PFS), duration of response (DOR), time to response (TTR), and overall survival (OS).
- Evaluate the safety and tolerability of repotrectinib in combination with trametinib.
- Characterize the PK profile of repotrectinib in combination with trametinib.

2.3. Exploratory Objectives (All Phases)

[figure not shown]
- Evaluate biomarkers potentially predictive of response in subjects treated with repotrectinib in combination with trametinib.
- Explore the potential prognostic utility of genomic alterations and characterize intrinsic or acquired resistance in subjects treated with repotrectinib in combination with trametinib using tissue-based or liquid-based biopsy samples.

3. STUDY DESIGN

3.1. Overall Study Design

This subprotocol is a Phase 1b/2 multi-center, open-label study to evaluate the efficacy, safety, tolerability, and PK of repotrectinib in combination with trametinib, for the treatment of subjects with locally advanced or metastatic *KRAS*^{G12D}-mutant solid tumors. The study will consist of two portions: Phase 1b Dose Escalation and Phase 2 Expansion (Figure 9).

Figure 9: Subprotocol 1 Study Design

Abbreviations: KRAS = Kirsten rat sarcoma viral oncogene homolog; MEK = mitogen-activated extracellular signal-regulated kinase; NSCLC = non-small cell lung cancer; RP2D = recommended Phase 2 dose.

3.2. Phase 1b Dose Escalation Study Design

The Phase 1b dose escalation portion of the study will follow a traditional 3+3 design, where three to six DLT-evaluable subjects with locally advanced or metastatic *KRAS*^{G12D}-mutant solid tumors will be enrolled at each dose level to determine the MTD/RP2D of repotrectinib in combination with trametinib through assessment of DLTs.

Initially, approximately 24 – 30 subjects with locally advanced or metastatic solid tumor malignancies harboring a *KRAS*^{G12D} mutation will be enrolled into the Phase 1b dose escalation portion. Three to six DLT-evaluable subjects at each dose level will be administered daily (QD) doses of repotrectinib in combination with trametinib according to Table 2 (starting with Dose Level 1) and evaluated for DLTs during Cycle 1 (i.e., for 28 days). After the first 3 subjects have completed their first cycle of study treatment (Cycle 1), a safety evaluation will be conducted by a Safety Review Committee to determine if enrollment of subjects in the next dose level (Dose Level 2) may begin. If no subjects experience a DLT within the first 28 days of Dose Level 1 treatment, then dose escalation may proceed to the next dose level, according to Table 2. If 1 of the 3 initial subjects at Dose Level 1 experiences a DLT, then the next 3 subjects will be enrolled prior to escalating to the next dose level. Enrollment into all subsequent dose levels will follow

the same procedure. If $\geq 33\%$ of subjects at any dose level experience a DLT within the first 28 days of treatment, the dose levels will be de-escalated to Dose Level -2 or -3 according to SRC recommendation and following approval by the Sponsor, as detailed in [Table 2](#). If Dose Level -2 is tolerable, testing of alternate escalating dose levels (-2a, -2b) may occur as outlined in [Table 2](#). If Dose Level -2 is not tolerable, subjects will be de-escalated to Dose Level -3. If Dose Level -3 is tolerable, testing of alternate escalating dose levels (-3a, -3b) may occur as outlined in [Table 2](#). Alternative regimens or additional dose levels or dose level increments may be explored based on emergent clinical safety, efficacy, and PK data. See [Section 3.2.1.1](#) for criteria for determining DLTs. The decision to escalate to the next dose level will be based on the incidence of DLTs and the totality of clinical data including overall PK, safety, and preliminary efficacy observed within each dose level.

Table 2: Dose-finding Dose Levels

Dose Level	Repotrectinib	Trametinib
3	160 mg QD/BID ^a	2 mg QD
2	160 mg QD	2 mg QD
1 (Starting Dose)	120 mg QD	2 mg QD
(-2b)	160 mg QD/BID ^a	1.0 mg QD
(-2a)	160 mg QD	1.0 mg QD
-2	120 mg QD	1.0 mg QD
(-3b)	160 mg QD/BID ^a	0.5 mg QD
(-3a)	160 mg QD	0.5 mg QD
-3	120 mg QD	0.5 mg QD

Abbreviations: BID = twice daily; QD = once daily.

^a 160 mg QD (once daily) for the first 14 days, after which the dose may be increased to 160 mg BID based on subject safety and tolerability and assuming specific criteria are met. Subjects must meet the following criteria while on 160 mg QD prior to dose increase to 160 mg BID: no evidence of grade ≥ 3 TRAE, unmanageable grade ≥ 2 dizziness, ataxia or paresthesia; or grade ≥ 3 clinically significant lab abnormalities.

A Safety Review Committee, including study Investigators and the Sponsor Medical Monitor, will provide recommendations for dose escalation, confirmation of DLTs, dose de-escalation, and determination of the RP2D ([Section 3.2.1.3](#)). At least 6 subjects will be treated at the RP2D prior to proceeding into the Phase 2 portion of the study. Additional subjects may be added at a dose level to gather more safety, PK, and efficacy data ([Section 3.2.1.3](#)).

To fully characterize the safety of the combination of repotrectinib and trametinib, subjects who are discontinued from treatment before completing the DLT evaluation period (28 days, Cycle 1) due to disease progression or other event unrelated to repotrectinib or trametinib, or who did not adequately complete the PK evaluations within Cycle 1, may be replaced.

Tumor assessments will include all known or suspected disease sites. All radiographic efficacy endpoints will be assessed using Response Evaluation Criteria in Solid Tumors (RECIST) v1.1. Intracranial responses will be assessed by modified RECIST v1.1. For all tumor assessments, the imaging modality used at baseline should be the same modality used throughout the study.

Safety will be monitored *via* laboratory assessments, physical examinations, ECGs, vital signs, and TEAEs according to CTCAE v5.0. PK data will also be collected.

An end of treatment (EOT) visit will be conducted within 7 days of the last dose of both study drugs. A safety follow-up visit will be conducted within 28 days of last dose of both study drugs. Additionally, to assess overall survival status, each subject will be contacted via phone call (or medical chart review), including information about subsequent anticancer therapies (including best response), every three months after discontinuation of study drugs until death, loss to follow-up, or withdrawal of consent, whichever occurs first.

3.2.1.1. Dose-Limiting Toxicities

Subjects are eligible for DLT evaluation if they experience a DLT during the first cycle of treatment (i.e., 28 days) or do not experience a DLT during the first cycle of treatment while able to receive at least 75% of planned doses during the first cycle of treatment. Subjects who do not fulfill these requirements will be replaced for DLT evaluation but will remain in the overall safety and efficacy analyses.

A DLT is defined as an AE or abnormal laboratory value assessed as unrelated to disease progression, intercurrent illness, or concomitant medications that meets any of the criteria in [Table 3](#).

Table 3: CTCAE Dose-Limiting Toxicities

Category ^a	Criteria
Toxicities resulting in an excessive number of missed doses	
 Inability to deliver at least 75% of the planned doses of repotrectinib and trametinib during Cycle 1 treatment because of toxicity attributed to study drug (excluding toxicities clearly related to disease progression or intercurrent illness)
Hematologic toxicities	
 Grade \geq 4 neutropenia ($\text{ANC} < 500/\text{mm}^3$) lasting > 7 days Grade \geq 4 platelet count decrease (platelets $< 25,000/\text{mm}^3$) or Grade ≥ 2 ($< 75,000/\text{mm}^3$) associated with clinically significant bleeding Grade \geq 4 anemia Grade \geq 3 febrile neutropenia (defined as $\text{ANC} < 1,000/\text{mm}^3$ with a single temperature of $\geq 38.3^\circ\text{C}$ [$\geq 101^\circ\text{F}$] or a sustained temperature of $\geq 38^\circ\text{C}$ [$\geq 100.4^\circ\text{F}$] for > 1 hour)
Renal	
 Grade \geq 3 creatinine increase ($> 3 \times$ upper limit of normal [ULN])
Hepatic	
 Grade \geq 3 total bilirubin elevation ($> 3 \times$ ULN) Grade \geq 2 total bilirubin elevation ($> 1.5 \times$ ULN) and grade ≥ 2 ALT or AST elevation ($> 3 \times$ ULN) Grade 3 ALT elevation ($> 5 \times$ ULN) that does not resolve to grade ≤ 1 within 7 days or any grade ≥ 4 ALT elevation Grade 3 AST elevation ($> 5 \times$ ULN) that does not resolve to grade ≤ 1 within 7 days or any grade ≥ 4 AST elevation Grade 4 elevations in ALP
Pancreatic	
 Grade \geq 3 amylase or lipase elevation
Cardiac	
 Grade \geq 3
Other AEs	
 Grade 3 electrolyte disturbances that require hospitalization Grade 4 electrolytes abnormalities Grade ≥ 3 AE, persisting after optimal treatment with standard medical therapy except for the exceptions noted below under “Exceptions to DLT criteria” In view of the Investigators and Sponsor, any other unacceptable toxicity encountered
Exceptions to DLT criteria	
 Grade 3 elevations in ALP Grade 3 electrolytes abnormalities that are adequately managed by IV or PO supplementation as evidenced by an improvement to grade ≤ 1 within 3 days Grade 3 fatigue which resolves to grade ≤ 1 in ≤ 7 days Isolated grade 3 laboratory abnormalities that are not associated with clinical sequelae and are corrected with supplementation/appropriate management within 72 hours of their onset Grade 3 dizziness which resolves to grade ≤ 1 within ≤ 7 days

Abbreviations: AE = adverse event; ALP = alkaline phosphatase; ALT = alanine aminotransferase; ANC = absolute neutrophil count; AST = aspartate aminotransferase; CTCAE = Common Terminology Criteria for Adverse Events, v5.0; DLT = dose-limiting toxicity; IV = intravenous; PO = per os (by mouth); ULN = upper limit of normal.

Toxicities clearly related to disease progression or intercurrent illness will not be considered DLTs.

In addition, clinically important or persistent toxicities not included in the above criteria may be considered a DLT following review by the Sponsor and study Investigators. All DLTs should represent a clinically significant shift from baseline. These will be evaluated according to National Cancer Institute CTCAE v5.0.

To fully characterize the safety of repotrectinib in combination with trametinib, subjects who are discontinued from treatment before completing the DLT evaluation period (28 days, Cycle 1) due to disease progression or other event unrelated to study drugs, or who did not adequately complete the PK evaluations within Cycle 1, may be replaced.

Dose re-escalation for subjects with DLTs is not allowed in the Phase 1b portion of the study. Subjects experiencing a DLT may resume dosing at the next lower dose level (if applicable) once adequate recovery is achieved.

3.2.1.2. Determination of MTD

The MTD is defined as the highest dose level of repotrectinib given in combination with trametinib observed to cause a DLT in fewer than 33% of the treated subjects in the first treatment cycle (i.e., 28 days, Cycle 1).

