9.1.3. Safety Analysis Set

The Safety Analysis Set includes all enrolled subjects who receive at least one dose of either study drug. This will be the same as the FAS. Subjects will be classified according to the actual treatment (dose levels or cohorts). Each subject will be classified into and analyzed consistently within one treatment group, unless otherwise specified.

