9.3. Study Endpoints

9.3.1. Primary Endpoint for Phase 1

- Incidence of first cycle (28 days) DLTs to determine MTD and/or RP2D.

9.3.2. Secondary Endpoints for Phase 1

- ORR assessed by the Investigator using RECIST v1.1
- Pharmacokinetic parameters of repotrectinib
- Pharmacokinetic parameters of trametinib

9.3.3. Primary Endpoint for Phase 2

- ORR assessed by Investigator using RECIST v1.1.

9.3.4. Secondary Endpoints for Phase 2

- DOR, TTR, and CBR by the Investigator
- Intracranial objective response rate (IC-ORR) assessed according to modified RECIST v1.1 in subjects with brain metastases
- PFS and OS
- Type, incidence, severity, timing, seriousness, and relatedness (to each study drug) of AEs and laboratory abnormalities
- Pharmacokinetic parameters of repotrectinib

- Pharmacokinetic parameters of trametinib

9.3.5. Exploratory Endpoints for Phase 1b and Phase 2

- ORR and PFS by modulation of circulating tumor levels and genomic alterations observed pre- and post-dosing.

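### The MTD definition divides DLTs by treated rather than DLT-evaluable subjects, so one non-evaluable subject can turn a failing 2/6 into a qualifying 2/7

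*Combined protocol and SAP*

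**What the plan says.** Section 3.2.1.2, repeated in the synopsis, makes the MTD the highest level "observed to cause a DLT in fewer than 33% of the treated subjects in the first treatment cycle".

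The rest of the dose-finding plan counts a different group:

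- Section 3.2: the escalation "will follow a traditional 3+3 design, where three to six DLT-evaluable subjects" are enrolled at each level. Section 9.2.1.1 uses the same unit.
- Section 3.2.1.1, evaluability: "Subjects are eligible for DLT evaluation if they experience a DLT during the first cycle of treatment", or if they have no DLT and could receive at least 75% of planned Cycle 1 doses.
- Section 3.2.1.1, replacement: "Subjects who do not fulfill these requirements will be replaced for DLT evaluation but will remain in the overall safety and efficacy analyses".
- Section 9.1.3: "The Safety Analysis Set includes all enrolled subjects who receive at least one dose of either study drug". A replaced subject therefore remains a treated subject in the ordinary sense.

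Two decision rules stand next to each other in Section 3.2 and the synopsis. The first is "If 1 of the 3 initial subjects at Dose Level 1 experiences a DLT, then the next 3 subjects will be enrolled" before escalation, and later levels follow the same procedure. The second has a threshold of at least 33% and reads, in part, "of subjects at any dose level experience a DLT within the first 28 days of treatment, the dose levels will be de-escalated". The move is to one of the two lower trametinib doses, on the Safety Review Committee's recommendation and with sponsor approval. This rule names neither a minimum cohort size nor an evaluable denominator.

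The Phase 1 primary endpoint in Section 9.3.1 is "Incidence of first cycle (28 days) DLTs to determine MTD and/or RP2D".

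**The concern.** The MTD is decided on one denominator and the cohorts are built on another. No section says that *treated* means *DLT-evaluable* in the MTD definition, and none overrides the word.

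The mismatch runs in one direction. A subject with a Cycle 1 DLT is evaluable by definition, so a non-evaluable subject has had none. The treated-based rate can equal the evaluable-based rate or fall below it, but can never exceed it. Taken literally, the definition can only make a level look more tolerable, and it matters at the result where a 3+3 normally stops, 2 of 6.

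The de-escalation sentence does not settle this, because its own denominator is unspecified. If it too means treated subjects, 2/7 does not trigger it.

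At stake is the Phase 1 primary endpoint. Section 3.2.1.3 sets the RP2D at or below the MTD, and about 50 Phase 2 subjects are to be treated at the RP2D.

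**Working it through.** The plan gives no operating characteristics for the 3+3, so there is no calculated figure to reproduce. The threshold is set by rule.

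**1. Does the 33% cut-off give the usual 3+3 boundary on an evaluable basis?** Yes. 1/6 = 16.7% qualifies; 2/6 = 33.3% is not below 33% and fails.

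**2. What do non-evaluable subjects change?** Each adds 1 to the denominator and 0 to the numerator.

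| Evaluable result | None | One non-evaluable | Two non-evaluable |
|---|---|---|---|
| 2/6 | 33.3%, fails | 2/7 = 28.6%, qualifies | 2/8 = 25.0%, qualifies |
| 3/6 | 50.0%, fails | 3/7 = 42.9%, fails | 3/8 = 37.5%, fails |
| 2/3 | 66.7%, fails | 2/4 = 50.0%, fails | 2/5 = 40.0%, fails |

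With one or two non-evaluable subjects, only 2/6 is reversed. Three DLTs would need four of them (3/10 = 30.0%).

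**3. How often could a level reach 2/6 with at least one non-evaluable subject?** The documents give neither DLT nor non-evaluability rates, so both are assumed. Let p be the true DLT rate among evaluable subjects and q the chance that a treated subject is non-evaluable, taken as independent of the evaluable subjects' outcomes.

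- A = P(1 DLT in the first 3, then 1 in the next 3) = [3p(1−p)²]². For p = 0.1, 0.2, 0.3, 0.4: 0.0590, 0.1475, 0.1945, 0.1866.
- B = P(at least one non-evaluable before 6 evaluable) = 1 − (1−q)⁶. For q = 0.05, 0.10, 0.20: 0.2649, 0.4686, 0.7379.
- Joint probability per level = A × B:

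| True DLT rate | q = 5% | q = 10% | q = 20% |
|---|---|---|---|
| 10% | 1.6% | 2.8% | 4.4% |
| 20% | 3.9% | 6.9% | 10.9% |
| 30% | 5.2% | 9.1% | 14.4% |
| 40% | 4.9% | 8.7% | 13.8% |

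**4. Which rows describe a level that should fail?** By the plan's own 33% threshold, only the 40% row. There the ordinary chance of passing (0/3, or 1/3 then 0/3) is 0.6³ + 3(0.4)(0.6²)(0.6³) = 0.216 + 0.432 × 0.216 = 30.9%. Adding the joint probability gives 30.9% + 4.9% = 35.8% at q = 5% and 30.9% + 13.8% = 44.7% at q = 20%, if the literal denominator is applied.

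**5. The de-escalation sentence.** 1/3 = 33.3% meets a threshold of at least 33%, although the rule just before it sends 1 of 3 to expansion. Read literally, this error is on the cautious side.

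**The case against.** The strongest reply is that the intent is plain. Section 3.2.1.1 takes the non-evaluable subject out of the DLT assessment, cohorts are counted as evaluable throughout, and a traditional 3+3 rejects 2 of 6. Decisions are not mechanical either. The Safety Review Committee confirms DLTs and recommends escalation and the RP2D, and Section 3.2.1.3 bases the RP2D on all the data. Appendix 2 records that the committee recommended de-escalation from Dose Level 1 on data from 2 patients. These points limit the harm. They do not supply a different definition, and if the intent is an evaluable denominator, the edit costs the sponsor nothing it wants.

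Several further points stand:

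- A reader might take 1.6% to 14% as the chance of declaring a wrong MTD. It is not: both ends come from true rates (10% and 30%) below the plan's threshold.
- Missing the 75% dose requirement because of drug toxicity is itself a DLT, so q covers other causes only. The documents offer no support for a value as high as 20%.
- A reader might infer that any 2/7 is a defect. It is not. Subjects may be added at a level, or replaced only for inadequate Cycle 1 PK while remaining DLT-evaluable. A 2/7 among evaluable subjects is a valid result under the below-33% rule.
- The absence of a DLT-evaluable set from Section 9.1 is weak evidence, because Sections 9 and 9.4.1 leave full analysis detail to a SAP.
- A reader might infer that the de-escalation sentence forces a retreat at 1 of 3. The expansion rule directly before it shows otherwise, so that point is minor.

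**Conclusion.** The concern holds as a wording defect in the MTD definition that is worth correcting. As written, one treated and replaced non-evaluable subject changes 2 DLTs in 6 evaluable subjects from failing (33.3%) to qualifying (28.6%), and the effect can only run toward tolerability. The ratios need no assumptions. The frequencies do: they rest on assumed DLT and non-evaluability rates, on independence between them, and on 2/6 arising as 1 of 3 followed by 1 of 3.

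For a level truly above 33%, the relevant range is 4.9% to 13.8% (true rate 40%). Even that supposes that the committee applies the literal denominator. The documents do not support saying that the plan would carry an intolerable dose into Phase 2. The definition raises the ceiling under which the RP2D is chosen; it does not choose it.

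**What to change.** In Section 3.2.1.2 and the synopsis, replace treated subjects with DLT-evaluable subjects in the MTD definition. DLT-evaluable subjects who are added to a level, or replaced only for PK reasons, stay in the count.

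As a minor alignment, restate the rule in Section 3.2 and the synopsis in counts of DLT-evaluable subjects:

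- 1 DLT in 3 expands the level to 6.
- 2 or more DLTs among 3 to 6 lead to de-escalation.
- If more than 6 are evaluable, at least 33% of them leads to de-escalation.

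The cost is an amendment to wording. Section 3.2.1.1 already requires replacement of non-evaluable subjects, so the change of denominator adds no subjects and no procedures.
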